Contextually, our community partners (CP; see letters of support) will be members of the community workgroup (CWG) and will play a central role throughout the process to improve the social validity^{31,34} and feasibility of the innovation while considering factors such as leadership, experience with adopting and implementing interventions, and organizational context and cultural relevance. **Facilitation** of the **innovation** within the **practice context** will be guided by the research team using a consultee-centered training approach³⁵ as we have in the past³⁶. We will use automated implementation of intervention content to ensure high fidelity (IVR calls) and keep implementation complexity low to address delivery system barriers (i.e. lack of resources, knowledge and training)³⁷ and L/H families participation barriers (i.e. lack of public transportation and cultural relevance, family and work responsibilities)³⁷, while targeting preferences for information receipt (i.e. verbal and written²²). RE-AIM³³ will provide guidance on the outcomes (Figures 1 and 3) to ensure our innovation addresses issues of scalability at the individual and organizational level as well as the resources, infrastructure, and flexibility necessary for future implementation. Finally, cultural adaptation is an important part of the implementation process¹⁶. As such, we will make adaptations guided by a theory-driven approach that is both **selective** (focuses on areas with poor fit among L/Hs in rural communities) and **directed** (aimed at improving engagement and outcomes)^{31,38}. We hypothesize that by incorporating community-informed

design features that tend to the cultural needs of L/H families, it will promote engagement and better outcomes independent of parents acculturation level.

INNOVATION

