
relevance (aim 1 measures) and acceptability identified in exit survey/interviews to determine whether intervention is appropriate for further testing. Qualitative Analysis. Qualitative interviews and FGs will be recorded and transcribed in English or Spanish. The PI, with assistance from [name] and [name] will construct the interview codebook, with inductive codes added iteratively by in-depth reading of transcriptions until saturation is achieved. Transcripts will be double-coded in NVivo by [name], [name] and the PI. Inter-coder reliability using Cohens kappa (goal > 0.80) will be assessed. The research team has extensive experience conducting qualitative investigation^{20,22,26,51,58,62,67}, possesses local linguistic expertise (Drs. [name] and [name], speak Spanish), and will be aided by bilingual (English-Spanish) CHW staff. Statistical Analysis: The association of the intervention with the primary outcome of proportion of children reducing BMI z-scores will be tested using a chi-square test. The degree of association will be summarized using the odds ratio. If the assumptions of the chi-square test are violated, Fishers exact test will be utilized. Potential gender, and acculturation scores (external and familial language use, and social relations) differences will be explored via stratification. Comparisons between groups within gender will be done using Fishers exact test. Secondary aims outcomes include parent BMI, waist, PA, sweet beverages intake and eating behaviors, home environment changes and quality of life. The quantitative outcomes will be summarized using means and standard deviations or medians and inter-quartile ranges, as appropriate. If categorized, outcomes will be summarized using counts and percentages. Between group differences at 6-month will be capture using ANCOVA with the baseline measure as the covariate. If the ANCOVA assumptions are violated, a t-test (or if indicated, Wilcoxon's sum rank test) between group change scores (6-month baseline measure) will be used. Potential parental engagement (% of reach, retention and completion) and acculturation scores (language and media use, and social ethnic relations) differences will be explored via stratification. Comparisons between groups will be done using Fishers exact test. Significance level is 0.05.

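### No planned analysis estimates whether the FC effect varies with parents' acculturation, so the hypothesis of independence from acculturation cannot be supported

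*Combined protocol and SAP*

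**What the plan says.** **The hypothesis.** Section 3 (Background and Rationale, Conceptual Framework) expects that attending to families' cultural needs means "it will promote engagement and better outcomes independent of parents acculturation level".

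**Section 12.B, Specific Aim 2, Statistical Analysis.** The "primary outcome of proportion of children reducing BMI z-scores will be tested using a chi-square test". Acculturation then appears twice.
- After the primary outcome: "Potential gender, and acculturation scores (external and familial language use, and social relations) differences will be explored via stratification". The measures table shows that these are subscales of the child's instrument. The test sentence that follows names gender only: "Comparisons between groups within gender will be done using Fishers exact test".
- After the secondary outcomes, with the parent's subscales: "acculturation scores (language and media use, and social ethnic relations) differences will be explored via stratification". Parental engagement is stratified in the same sentence. Next comes "Comparisons between groups will be done using Fishers exact test. Significance level is 0.05". The outcome and the groups for these tests are not specified.

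**Section 12.E, Statistical Analysis.** A mixed model for BMI z-score admits participant-level covariates and makes the treatment coefficient the quantity of interest. It has no treatment-by-acculturation term. Acculturation is listed there among the additional outcomes for ANCOVA.

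No section gives an interaction test, a stratum cut-off, power by stratum, or a rule for concluding that benefit is independent of acculturation.

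**The concern.** Independence from acculturation is a statement about effect modification: the difference between FC and standard care (SC) should be much the same in less and more acculturated families. Evidence on it requires an estimate of how much that difference changes, with its uncertainty. The plan produces no such estimate.

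The nearest planned analysis, Fisher tests by stratum, answers another question. A significant result in one stratum and not in the other does not show that the effects differ. Two non-significant results do not show that they agree.

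The direction of the error also matters. The investigators' expectation coincides with the statistical null, so small strata favour it. Whether benefit depends on acculturation bears directly on a cultural adaptation and on which families a later trial should target.

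**Working it through.** **Inputs from the documents**
- Sections 12.B and 12.E (Sample Size Calculation): 46 evaluable dyads, 23 per group; 58 recruited, 29 per group; 80% power; alpha 0.05.
- Section 12.E: difference 0.05 BMI z, SD 0.06.
- Section 12.B measures table: parental acculturation total score and a low/high rank, collected at baseline.

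**Assumptions, because the documents give no figure:** an even low/high split; the response proportions below; SD 0.06 in every cell; two-sided tests.

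**Step 1: reproduce the plan's figure.** n per group = 2 × (1.96 + 0.8416)² × (0.06/0.05)² = 2 × 7.849 × 1.44 = 22.6, so 23. This agrees with the plan. It is sized for the main effect only.

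**Step 2: cell sizes.** An even split gives 23/2 = 11.5 dyads per arm per stratum at 46, and 29/2 = 14.5 at 58. Cells of 11 to 15 cover both.

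**Step 3: Fisher tests of FC against SC within each stratum.** FC works in one stratum only, and the other stratum has the SC rate in both arms. Power and size come from exact enumeration. P(both non-significant) = (1 − power) × (1 − size).

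| Rates where FC works | n per cell | Power | Size in other stratum | Both non-significant |
|---|---|---|---|---|
| 60% v 30% | 11 | 16.5% | 1.4% | 82% |
| 60% v 30% | 15 | 22.7% | 1.7% | 76% |
| 70% v 40% | 11 | 16.5% | 1.6% | 82% |
| 70% v 40% | 15 | 22.7% | 1.6% | 76% |
| 70% v 30% | 11 | 31.6% | 1.4% | 68% |
| 80% v 40% | 15 | 44.7% | 1.6% | 54% |
| 80% v 30% | 11 | 52.1% | 1.4% | 47% |
| 80% v 30% | 15 | 68.0% | 1.7% | 32% |

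First row worked: (1 − 0.165) × (1 − 0.0144) = 0.823. The pair of tests misses the pattern most of the time at 30 points and more often than not at 40, but not at 50.

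**Step 4: precision of a direct interaction on BMI z, low versus high.** SE = 0.06 × √(4/n per cell); half-width = t × SE.
- 46 dyads: SE = 0.06 × √(4/11.5) = 0.06 × 0.590 = 0.0354; t (42 df) = 2.018; half-width 0.071.
- 58 dyads: SE = 0.06 × √(4/14.5) = 0.06 × 0.525 = 0.0315; t (54 df) = 2.005; half-width 0.063.

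Both exceed the planned effect of 0.05. If FC had its full effect in one stratum and none in the other, the interaction test would have 28.2% power at 46 dyads and 34.4% at 58. With a 70/30 split at 46 it would have 24.4%.

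**Step 5: the same for the proportion reducing BMI z.** Half-width of the difference in risk differences = 1.96 × √(Σp(1 − p)/n per cell).
- 11 per cell, rates 60/60/40/40: 1.96 × √(0.96/11) = 58 points.
- 14.5 per cell, rates 70/70/40/40: 1.96 × √(0.90/14.5) = 49 points.

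**The case against.** The strongest reply is that this is one sentence in a background section of a feasibility study. The Aim 2 hypotheses in Section 2 do not mention acculturation, Section 12.B calls the stratification exploratory, and the sentence could mean a benefit after adjustment for acculturation, which the covariates in Section 12.E would allow. This stands as a limit on how serious the point is. It does not supply the missing analysis: adjusting for acculturation does not show whether the effect varies with it.

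Three stronger readings are tempting and are not supported.
- A reader might infer that the trial will declare independence when the Fisher tests are non-significant. The documents state no such rule. They link no analysis to the hypothesis and leave that reading open.
- A reader might infer that Fisher's test by acculturation is planned for the primary outcome. The sentence attached to that outcome names gender only, and the acculturation scores beside it are the child's. The later sentence follows parental acculturation but names no outcome, so Step 3 illustrates what stratified tests could show rather than a fully specified plan.
- A reader might infer that any large difference would usually be missed. That depends on what counts as large: it fails at 50 points.

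It is also fair to say that an interaction test is weak at this size. Its merit is that it estimates the right quantity and shows the uncertainty; it does not rescue power.

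**Conclusion.** The point holds as a gap between a stated hypothesis and the planned analysis. No planned analysis estimates how the FC effect changes with parental acculturation. Stratified Fisher tests would be jointly non-significant about 76-82% of the time for a 30-point benefit confined to one stratum, and 54-68% for 40 points, so their non-significance is not evidence of independence.

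These percentages rest on an assumed even split and assumed response rates. The half-widths of 0.063-0.071 BMI z rest on the plan's SD of 0.06 and an even split, without any precision gained from baseline adjustment. On those assumptions the trial cannot resolve the hypothesis by any method. The primary comparison is unaffected.

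**What to change.** 1. In the Statistical Analysis parts of Sections 12.B and 12.E, replace the acculturation-stratified Fisher tests with one pre-specified, exploratory arm-by-baseline parental acculturation interaction. Use the continuous total score, expressed per SD, in the ANCOVA or mixed model for BMI z-score.
2. For the proportion reducing BMI z, report the matching difference in risk differences between the low and high ranks.
3. Report each estimate with a 95% confidence interval.
4. State that a non-significant result will not be read as independence, for outcomes or for engagement, and that 46 to 58 dyads cannot resolve the hypothesis in Section 3.
5. Set no equivalence margin. A margin of 0.05 BMI z would be practically unattainable, since the half-width exceeds it even for an estimate of exactly zero. It also has no defined meaning for a per-SD coefficient or for the binary outcome, and a margin as large as the whole planned effect would be hard to defend.

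**Cost.** Wording and slightly more analysis. The scores are already collected at baseline, so no added participants, visits or measures are needed. The downside is that the hypothesis will be reported as unresolved.

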
CHARACTERISTICS OF THE SUBJECT POPULATION

4. Accrual

A. Is this study conducted solely at sites under the oversight of the UNMC IRB (e.g.

UNMC, Nebraska Medicine, CHMC, UNO)?

Yes

1. How many subjects will need to be consented (per group, as applicable) in order to achieve the scientific objectives of the research?

The proposed study will involve approximately 272 (Aim 1=106, Aim 2=166) participants. Participants are required to complete study aims as described:

Aim 1:

We will involve 40 adults-parents from L/H families from the sampling region to participate in two rounds of focus groups (FG, n=80) with 6 parents taking part in usability tests (UT, n=6), and approximately 10 adults to participate in a Community Working Group (CWG, n=10) that will participate in two interviews (n=10).

Aim 2:

The parent-child dyads (n=116) include adults (19 years of age or older, n= 58) and their children (6-12 years of age, n=58) living in rural Nebraska over a period of 12 months and 2 different stages of the project randomized in two arms:

Standart Care= 29 dyads (58 participants)

FC intervention= 29 dyads (58 participants)

At the end of the intervention parents participating that participated in the intervention (FG, n=40) and CWG (n=10) will be invited to participate in focus groups for a post-program satisfaction and evaluation.

2. What is the statistical or other justification for the total number of subjects described above?

Aim 1 sample based in the literature recommended number per evaluation for focus group (5-10 participants) and usability tests (5 per test)⁷⁴.

Intervention testing sample size is based on the comparison of changes in BMI z-scores achieved by participants in FC-IVR with those achieved by participants in FC-workbook condition at 6 months post randomization14. A total of 56 (23 per group) parent-child dyads achieves 80% power (alpha 0.05) to detect a significant difference between the SC and IVR conditions, based on the relative BMI z-score differences (0.05) and standard deviation related to 6-month BMI z-score reduction for FC-IVR (0.06). To account for 25% rate at 12-month, we will recruit a total of 58 (29 per group) dyads.

5. Gender of the Subjects

A. Are there any enrollment restrictions based on gender?

No

6. Age Range of Subjects

A. Will adults be enrolled ?

Yes

1. What is the age range of the adult subjects?

19 years of age or older.

2. What is the rationale for selecting this age range?

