Specific Aim 2: To evaluate the feasibility and preliminary effectiveness of a technology-delivered FBCO intervention for L/H families in rural Nebraska using RE-AIM and i-PARIHS. We will randomly assign participants to either the intervention or an enhanced standard care group (Figure 3). Sample Size Calculation. Sample size is based on the comparison of changes in BMI z-scores achieved by participants in FC-IVR with those achieved by participants in FC-workbook condition at 6 months post randomization²⁰. A total of 46 (23 per group) parent-child dyads achieves 80% power (alpha 0.05) to detect a significant difference between SC and IVR groups conditions. To account for a 25% attrition rate at 6-month we will recruit a total of 58 (29 per group) dyads. Participant Recruitment and Baseline Assessment Procedures. [name] will coordinate the recruitment of the participants with the help of CHWs. We will recruit a total of 58 dyads (Table 1). Baseline visits will take place at local community centers using private rooms. Dyads will complete informed consent, height, weight and waist circumference assessments, as well as complete a computer-based survey. Randomization will follow a random-numbers table (families/staff unblinded). Standard-Care. Families randomized to this group will receive FC-workbook. No additional materials or intervention contact will be provided. CHWs will follow a retention protocol to ensure these individuals return to 6-month assessments. Intervention Delivery. Families randomized to this group will receive the adapted version of the intervention described above. Drs. [name] and [name] will monitor IVR completion reports and assist the student-worker and CHWs in the on-going monitoring and engagement of participants during the intervention. Measurements and Data Collection. All measures (see table at PHS section for description) will be collected prior to intervention initiation and at 6 months post baseline (Figure 3). Weight will be assessed using a digital scale calibrated for accuracy prior to each assessment period using standard weights of a known quantity (e.g., 100-pound dumbbell). Height will be measured with a stadiometer, calibrated in 0.1-cm intervals. Waist circumference will be measured with a spring-loaded cloth tape measure at the level of the iliac crest using the average of the two closest measurements. Other Measures. Children and parents will complete measures of physical activity^{98,99}, eating behaviors¹⁰⁰, beverage intake¹⁰¹, quality of life^{102,103} acculturation^{104,105}, and health literacy¹⁰⁶. Parents will also complete home environment¹⁰⁷ surveys. During the 6-month assessment parents will complete program satisfaction surveys and a short exit interview with a CHW. Feasibility will be assessed according to intervention relevant factors (RE-AIM dimensions, engagement, attendance and completion rates), cost-effectiveness, cultural

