Maintenance	
 - Characteristics of completers vs non-completers - Intention to continue the intervention - Qualitative feedback on barriers/facilitators from participants/staff and leadership using i-PARIHS constructs 	
 -Demographic and clinical data from intake surveys [SW, CHWs] -Clinical data forms at 0,12 months [CHWs] -Qualitative interviews with participants, facilitators, staff, and health authorities [[name] , PI [name]] 	

Sample Size Calculation. Sample size is based on the comparison of changes in BMI z-scores achieved by participants in FC-IVR with those achieved by participants in FC-workbook condition at 6 and 12-month post randomization. A total of 46 (23 per group)

parent-child dyads achieves 80% power (alpha 0.05) to detect a significant difference between the FC-workbook and FC-IVR conditions, based on the relative BMI z-score differences (0.05) and standard deviation related to 6-month BMI z-score reduction for FC-IVR (0.06). To account for 25% attrition rate at 12-month, we will recruit a total of 58 (29 per group) parent-child dyads.

Cost Analysis: Costs will be assessed using time tracking spreadsheets and focused primarily on Aim 2 as it relates to the intervention delivery, though costs of participant recruitment will also be tracked using material and staff time to determine dollar amounts. [name] will complete A simple cost benefit analysis by assessing intervention implementation costs at 6-month post baseline by BMI z-scores reduction categories of unchanged, ≤ 0.1 , 0.1-0.25 and ≥ 0.25 , respectively.

Qualitative Analysis. Qualitative interviews will be recorded and transcribed in English or Spanish. The PI, with assistance from Drs. [name] and [name], will construct the interview codebook, with inductive codes added iteratively by in-depth reading of transcriptions until saturation is achieved. Transcripts will be double-coded in NVivo by [name]. Inter-coder reliability using Cohens kappa (goal > 0.80) will be assessed. The research team has extensive experience conducting qualitative investigation, possesses local linguistic expertise (Drs. [name] speak Spanish), and will be aided by community partners bilingual (English-Spanish) CHW staff.

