Statistical Analysis: Descriptive, parametric, and non-parametric statistical methods will be used to compare continuous and categorical variables among the intervention groups at baseline. Data will be examined for the presence of outliers, violations of normality (for those continuous variables) and missing data. Major violations of normality will be corrected with an appropriate transformation procedure or non-parametric methods . Multi-level mixed effect models will be employed to control errors of non-independence, heteroskedasticity caused by parent-child dyad heterogeneity, and potential covariates to control to detect the BMI z-score reduction differences between the two conditions. In its simplest form, the model generally can be shown as:

$$BMIZscore_{it} = \mu + \alpha_i + X_{ijt} \beta + W_i \sigma + TT_t + \theta d_i + T_t + v_{it}$$

All measures are obtained for 3 time periods: baseline, 6, and 12 months. The dependent variable is BMIZ score for participant i at time point t . The unobserved participant-level heterogeneity that is not time dependent is represented by α_i , is allowed to vary by parent-child-dyads and to be a random variable. The X_{it} are time-period-level covariates and the W_i are participant-level covariates. The model also contains treatment group indicators d_i , and

time period indicators T_t . Relative treatment effect between conditions will be captured by coefficient θ and is the variable of interest. Sensitivity analysis will be conducted to examine the robustness of the mixed effect model across different random-effect distribution specifications (e.g., normal, finite mixture of normal etc.). Additional outcomes (e.g., parent BMI, waist circumference, PA, sweet beverages intake and eating behaviors, acculturation, home environment changes and quality of life) will be analyzed using ANCOVA with the baseline measure as the covariate. If the ANCOVA assumptions are violated, a t-test (or if indicated, Wilcoxon's sum rank test) between group change scores (6 or 12 month measure and baseline measure) will be used. Significance level for all tests is 0.05. Analyses will be performed using R 3.6 (R Core Team).

F. Does this study involve the collection of blood, urine, saliva or other human biological material (HBM)?

No

DRUGS, BIOLOGIC DRUGS AND DEVICES

13. Drugs and Biologic Drugs

1. Does this research involve the use of drugs or biologics?

No

14. Devices

1. Does this research involve a medical device(s)?

No

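### Recruiting 58 dyads does not allow for the stated 25% attrition: 23 evaluable per group needs 31 recruited, not 29; one section also gives 56 for 46, and the 25% is placed at different visits

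*Combined protocol and SAP*

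**What the plan says.** The sample size is justified in three places. All three recruit 58 dyads (29 per group) against 23 evaluable per group, but they differ in detail.

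- **Section 12.B, Specific Aim 2, Sample Size Calculation:** 46 evaluable dyads for a comparison at 6 months, then "To account for a 25% attrition rate at 6-month we will recruit a total of 58 (29 per group) dyads".
- **Section 4.A.2 (justification of the number of subjects):** "A total of 56 (23 per group) parent-child dyads achieves 80% power (alpha 0.05"), for a comparison at 6 months, then "To account for 25% rate at 12-month, we will recruit a total of 58 (29 per group) dyads".
- **Section 12.E, Sample Size Calculation:** 46 evaluable dyads (23 per group) for a comparison at 6 and 12 months, then "To account for 25% attrition rate at 12-month, we will recruit a total of 58 (29 per group) parent-child dyads".

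The visit schedule is split in a similar way.

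- **Section 12.B, Measurements and Data Collection:** measures "will be collected prior to intervention initiation and at 6 months post baseline". The table of measures in that section has columns for baseline and 6 months only.
- **Section 12.E:** the Maintenance row of Table 1 lists "Clinical data forms at 0,12 months", and Statistical Analysis says "All measures are obtained for 3 time periods: baseline, 6, and 12 months".
- **Section 23.A:** families are compensated for three visits, at 0, 6 and 12 months.

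**The concern.** An attrition allowance should leave the evaluable target intact when the stated fraction of recruited dyads is lost. Here it does not: a quarter of 29 is more than 7, and 29 less 7 is 22, already below 23. In Section 12.B the conflict is direct, because the powered comparison and the 25% both sit at 6 months.

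Two further faults sit in the same text. In Section 4.A.2 the total and the per-group number disagree within one sentence. The three sections also do not agree on the visit to which the 25% belongs, and the documents do not settle whether a 12-month visit takes place. A reader therefore cannot tell which comparison the allowance is meant to protect.

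At stake is whether the plan's claim of 80% power after 25% attrition is true, and whether the number of subjects put to the IRB is justified as written.

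**Working it through.** **Inputs.** Difference in BMI z-score change 0.05 and SD 0.06 (Sections 4.A.2 and 12.E; Section 12.B gives neither). Power 80% and alpha 0.05 (all three sections). Allocation 29:29. Attrition 25%. The sample-size text states neither the sidedness of the test nor the method, so both are inferred from what reproduces the plan's 23.

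**Step 1: reproduce the evaluable target.** Standardised difference d = 0.05/0.06 = 0.833. On the two-sided normal approximation,

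n per group = 2 × (1.960 + 0.842)² / 0.833² = 22.6, so 23 (46 in total).

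This matches Sections 12.B and 12.E. A one-sided test gives 17.8, so 18, and does not match. A two-sided t-based calculation gives 23.6, so 24.

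**Step 2: reproduce the recruited number.**

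- Multiplying: 46 × 1.25 = 57.5, so 58; or 23 × 1.25 = 28.75, so 29 per group. This is the plan's figure.
- Dividing by the retained fraction: 23/(1 − 0.25) = 30.67, so 31 per group and 62 in total.

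The plan's figure arises only from multiplying. The shortfall against the stated allowance is 2 dyads per group, 4 in total.

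**Step 3: what 29 per group does protect.** 29 − 23 = 6, and 6/29 = 20.7% loss in each group. At 25% loss, 29 × 0.75 = 21.75 per group, or 58 × 0.75 = 43.5 dyads overall. In whole dyads this is 44 left (24.1% lost) or 43 left (25.9% lost).

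**Step 4: effect on power.** For the difference in means,

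power = Φ(0.05 / [0.06 × √(1/n₁ + 1/n₂)] − 1.960).

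The difference detectable with 80% power is (1.960 + 0.842) × 0.06 × √(1/n₁ + 1/n₂).

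| Evaluable dyads | Normal approximation | Noncentral t | Detectable difference (normal) |
|---|---|---|---|
| 23 / 23 | 80.7% | 78.9% | 0.0496 |
| 22 / 22 | 78.9% | 77.0% | 0.0507 |
| 21 / 22 | 78.0% | 76.0% | 0.0513 |

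Uneven losses change little on the normal approximation: 78.8% at 21/23, 78.6% at 20/24 and 77.8% at 20/23.

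**Step 5: the total in Section 4.A.2.** 2 × 23 = 46, not 56. Read literally, 56 evaluable would be 28 per group, and recruiting 29 would leave room for a loss of only 1/29 = 3.4%. The unchanged 23 per group and 58 recruited, together with 46 in the other two sections, mark 56 as a slip.

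**Step 6: the visit.** Section 12.B ties the 25% to month 6, and its schedule ends there. Sections 4.A.2 and 12.E tie it to month 12. Section 4.A.2 nevertheless powers a 6-month comparison, while Section 12.E powers comparisons at both visits. If 25% is the loss by month 12, the 6-month comparison still has 23 per group provided that loss by month 6 is no more than 20.7% in each group.

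**The case against.** The strongest reply is that a real shortfall is shown only under the Section 12.B reading. Where the 25% is a 12-month figure, the 6-month comparison may be fully covered. At month 12 the analysis in Section 12.E need not be restricted to completers: "Multi-level mixed effect models will be employed to control errors of non-independence", and such a model can use the 6-month data of a dyad missing at month 12. This stands. It limits the direct claim to Section 12.B and, at month 12, to the completer calculation as the plan writes it.

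A second reply is that the consequence is slight: 2 dyads per group and 1 to 2 points of power, in an aim concerned with feasibility and preliminary effectiveness. This also stands, and it is why the point is minor. It does not make the sentence true.

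A third reply concerns the power figure. The noncentral t gives 76.0–77.0% at the same loss, below the 78–79% of the normal approximation, and the fallback test in the plan is a t-test. In addition, the calculation concerns a difference in means, whereas Section 12.B names the proportion of children reducing their BMI z-score, tested by chi-square, as the primary outcome. Both remarks are fair. Any restated power should therefore name its method and the quantity it refers to. Neither affects the attrition arithmetic, the total of 56 or the conflict between 6 and 12 months, none of which depends on the choice of test.

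**Conclusion.** The concern holds, as a minor correction. In Section 12.B, 58 dyads do not account for 25% attrition at 6 months: 62 would, and 58 keep 23 per group only up to 20.7% loss in each. At 25% loss, power for the difference in mean BMI z-score change is about 78–79% rather than 80%. That figure rests on a two-sided test and the normal approximation, which are inferred because they reproduce 23. On the noncentral t it is 76–77%, but there the plan's own 23 per group gives 78.9% before any loss.

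The total of 56 in Section 4.A.2 is wrong as written. The placing of the 25% at 6 or at 12 months is an open contradiction, and it follows the wider disagreement about whether a 12-month visit exists.

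**What to change.** Enrolment need not change. In Sections 4.A.2, 12.B and 12.E:

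1. State 46 evaluable dyads (23 per group) throughout, correcting 56 to 46 in Section 4.A.2.
2. State once the visit to which the 25% applies, and reconcile it with the schedule: baseline and 6 months in Section 12.B and its table of measures, month 12 as well in Sections 12.E and 23.A.
3. Replace the allowance sentence with, for example: *Recruiting 58 dyads (29 per group) retains 23 per group for up to 20.7% attrition in each group; at 25% attrition about 43–44 dyads remain, and power for the difference in mean BMI z-score change is about 78–79% (two-sided test, normal approximation).*
4. The sponsor should confirm the sidedness and the method behind the 23. If a t-based calculation was intended, the power at 25% loss should read about 76–77%.

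The cost is wording in three paragraphs, with no change to enrolment, design or analysis. The one drawback is a slightly less favourable power statement at 25% attrition.
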